7. MILESTONES

Milestone	Planned Date
Final protocol	26 April, 2016
First Protocol amendment	6 September 2016
Start of data collection	6 April 2017
Second Protocol amendment	17 January 2018
Third Protocol amendment	13 June 2018
Fourth protocol amendment	01 Aug 2018
End of data collection	Until the last patient completes the follow up period
Registration in the EU PASS register	EUPAS17055
Final report of study results	6 months after the last patient out

8. RATIONALE AND BACKGROUND

Idiopathic pulmonary fibrosis (IPF) is a specific form of chronic, progressive, fibrosing interstitial pneumonia of unknown cause, occurring primarily in older adults. While IPF is the most common of the 7 major idiopathic interstitial pneumonias, it is a rare and fatal disease with a median survival time of 2 to 3 years following diagnosis [[P11-07084](#)]. The natural history of IPF is variable and unpredictable [[P12-03241](#)]. Disease progression is manifested by increasing respiratory symptoms, worsening pulmonary function test results, acute respiratory decline, or death.

Nintedanib is a small molecule tyrosine kinase inhibitor. It is an indolinone derivative that blocks the kinase activity of the fibroblast growth factor receptors (FGFR) 1-3, the platelet derived growth factor receptors (PDGFR) α and β , and the vascular endothelial growth factor receptors (VEGFR) 1-3 [[P08-08684](#)]. Theoretical and pharmacological models suggest that inhibition of these kinase receptors may interfere with the fibrotic signalling cascade.

Pharmaceutical treatments indicated for IPF are limited. Various pharmacologic options like corticosteroids, azathioprine, cyclophosphamide, and N-acetylcysteine are currently being used for the management of IPF, albeit none of these has been proven efficacious in clinical trials compared with placebo [[P11-07084](#)]. The only drug that has been registered in India for the treatment of IPF is Pirfenidone. The recommended dose of Pirfenidone is 1800-2400mg. Data suggests that lot of Indian patients do not tolerate Pirfenidone at the recommended doses [[P16-04690](#)]. Thus, despite the availability of Pirfenidone, the medical need for efficacious and safe treatment of IPF remains high.

In pooled data of the multicentre international phase III trials 1199.32 and 1199.34, treatment with Nintedanib 150 mg b.i.d. for 52 weeks significantly reduced the annual decline in FVC compared to placebo. The tolerability and safety of Nintedanib was comparable to placebo with a slightly higher incidence of AEs in the Nintedanib group compared to the placebo group. There was no difference in the proportion of patients experiencing serious adverse events between the treatment groups. The most commonly reported AEs were gastrointestinal disorders. Of those, the most frequent event was diarrhea. Most of these events were of mild or moderate intensity. Administration of Nintedanib was associated with liver enzyme (ALT, AST, ALP, and γ -GTP) and bilirubin elevations which were reversible upon dose reduction, treatment interruption or withdrawal. No Hy's law case was reported in patients treated with Nintedanib [[P14-07514](#)].

A total of 20 Indian patients in both trials (1199.32 and 1199.34) were administered Nintedanib 150 mg b.i.d. The safety and efficacy of Nintedanib in this small number of patients was in line with the global data [[c03113022-01](#)]. Indian regulatory authority (Drug Controller General of India) recommended the approval of Nintedanib for IPF patients with a waiver for a local clinical trial and a requirement for an active surveillance of all IPF patients prescribed with the drug to generate additional safety data. The proposed active surveillance aims to collect real world safety data of 200 patients treated with nintedanib per the approved label at selected centres after the commercial availability of the drug in India (23rd January 2017).

9. RESEARCH QUESTION AND OBJECTIVES

This active surveillance aims to collect the safety data of 200 IPF patients treated with nintedanib in approved indication after the commercial availability of the drug in India (23rd January 2017). The objective is to look at safety of nintedanib in the real world setting.

10. RESEARCH METHODS

10.1 STUDY DESIGN

200 IPF patients treated with nintedanib per the Indian label will be enrolled in this active surveillance program. They are classified into following groups:

- Group A. Patients who started treatment with nintedanib after 23rd January, 2017 and have permanently discontinued the drug (as decided by the investigator) at the time of participation in the active surveillance. Data for these patients will be collected in anonymized manner after getting approval from the Ethics Committees for data collection and sharing.
- Group B. Patients who started treatment with nintedanib after 23rd January, 2017 and are continuing the drug at the time of participation in the active surveillance.
- Group C. Patients who have been newly prescribed nintedanib at the time of participation in the active surveillance.

In addition 200 IPF patients treated with pirfenidone will also be enrolled. They are classified into following groups:

- Group I. Patients who started treatment with pirfenidone after the 23rd January, 2017 and have permanently discontinued the drug (as decided by the investigator) at the time of participation in the active surveillance. Data for these patients will be collected in anonymized manner after getting approval from the Ethics Committees for data collection and sharing.
- Group II. Patients who started treatment with pirfenidone after the 23rd January, 2017 and are continuing the drug at the time of participation in the active surveillance.
- Group III. Patients who have been newly prescribed pirfenidone at the time of participation in the active surveillance.

The medical records at the selected sites will be screened to enroll Group A and B patients in a retrospective manner. Group C patients will be enrolled prospectively. The first patient enrolled at a given site should be in the nintedanib group. Once a patient is enrolled into the nintedanib group, the site team is suggested to enrol the next eligible patient, who has initiated or will be initiating pirfenidone at the same site in the pirfenidone group.

The safety data for nintedanib treated patients will be collected for at least 52 weeks or till the discontinuation of the drug, whichever is earlier. Patients treated with pirfenidone will not be followed.

At visit 1, the baseline characteristics (e.g. demographics, pulmonary function tests, HRCT evaluation etc., see [section 10.3.3](#)) will be recorded for all patients (either treated with nintedanib or pirfenidone).

The medical records of patients belonging to Group A and B will be evaluated to see if any ADRs and SAEs have occurred in the nintedanib treated arm during the duration of the treatment/ 52 weeks, whichever is earlier. Group B and Group C patients will be followed up according to clinical practice

for at least 52 weeks /discontinuation (whichever is earlier) from the start of the treatment at regular intervals (i.e. approximately every 4 weeks for the first 3 visits and approximately every 12 weeks thereafter till week 52). At each visit, all ADRs associated with nintedanib and SAEs will be recorded and reported per [section 12.2](#). In case a patient discontinues nintedanib before 52 weeks, all ADRs and SAEs will be collected till the date of discontinuation of nintedanib. There may be unscheduled visits between the scheduled visits. All ADRs and SAEs will also be collected at these unscheduled visits and entered into the eCRF. For nintedanib treated patients, certain information (e.g. co-medications, see [flowchart](#)) will also be collected at further and unscheduled visits (if available), as the status may change over time.

In case the patient is lost to follow up (patients not contactable for further visits), the site should attempt to contact the patient or patient's relative telephonically to gather the information on the vital status and record it in the eCRF.

Additionally, whenever the investigator becomes aware of SAEs and/or ADRs occurring in an enrolled patient before individual patient's end of study and it needs to be reported as per [section 12.2](#).

Patients who have taken at least one dose of nintedanib will be included in the safety analysis.

As this is an active surveillance of patients treated with nintedanib in the real world setting, no specific treatment is mandated or withheld from the patients. The choice of maintenance treatment for IPF must be according to the regular medical practice and at the discretion of the physician. The assignment of the patient to nintedanib or any other treatment falls within current practice and prior to the decision to talk to the patient about the study, so that the decision to prescribe nintedanib is clearly separated from the decision to include the patient in this active surveillance program. The decision of treatment, including the intended duration of treatment, is at the discretion of the physician providing care for the patient.

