10.2.2 Selection of population

10.2.2.1 Inclusion / exclusion criteria

Inclusion criteria for nintedanib treated patients:

Inclusion criteria:

1. Patients with documented diagnosis of IPF based upon ATS/ERS/JRS/ALAT 2011 guidelines (nintedanib naïve or pirfenidone pre-treated) who have initiated or will initiate nintedanib according to the package insert after the commercial availability of drug in India (23rd January 2017).
2. Patients in whom it is possible to obtain voluntary informed consent either from the patient or patient's legally authorised representative (applicable for Group B and C patients, see [section 10.1](#) for details).

Proprietary confidential information © 2018 Boehringer Ingelheim International GmbH or one or more of its affiliated companies

3. Patients in whom data collection is possible from the medical records (applicable for Group A and B patients, see [section 10.1](#) for details).
4. Patients in whom information on baseline characteristics mentioned in the [section 10.3.3](#) is available.

-Exclusion criteria:

1. Patients who were previously treated with nintedanib.
2. Patients who have initiated or will initiate nintedanib concomitantly with pirfenidone.
3. Patients who are participating in a clinical trial.

Inclusion criteria for pirfenidone treated patients:

Inclusion criteria:

1. Patients with documented diagnosis of IPF based upon ATS/ERS/JRS/ALAT 2011 guidelines (antifibrotic naïve) who have initiated or will initiate pirfenidone according to the package insert after the commercial availability of nintedanib in India (23rd January 2017)
2. Patients in whom it is possible to obtain voluntary informed consent either from the patient or patient's legally authorised representative (applicable for Group II and III patients, see [section 10.1](#) for details).
3. Patients in whom data collection is possible from the medical records (applicable for Group I and II patients, see [section 10.1](#) for details).
4. Patients in whom information on baseline characteristics mentioned in the [section 10.3.3](#) is available.

Exclusion criteria:

1. Patients who were previously treated with nintedanib or pirfenidone.
2. Patients who have initiated or will initiate pirfenidone concomitantly with nintedanib.
3. Patients who are participating in a clinical trial.

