10.9 LIMITATIONS OF THE RESEARCH METHODS

The scientific objective of this active surveillance is to obtain an estimate of the occurrence of all ADRs and SAEs in IPF patients prescribed Nintedanib per the approved label in the real world setting. For retrospective data, there may be a possibility of missed information on adverse events. For patients followed prospectively, lost to follow up, loss of information and recall bias could impose limitations. Since only the cohort treated with Nintedanib will be followed up, it is impossible to assess the safety of Nintedanib compared to other drugs. The possible selection bias will be minimised by enrolling all patients who have initiated or will initiate nintedanib (Group A, B and C) from the date of commercial availability of drug (23rd January 2017) at selected centres and potential channelling bias will be assessed by recording the baseline characteristics of a comparator group of equal number of patients who have been treated with pirfenidone.

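### Deaths on nintedanib before enrolment have no clear place in Protocol 10.1 and no route into the SAP's analysis sets, while survivors' time is counted from treatment start, so the fatal and total SAE rates are biased downward

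*Protocol*

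**What the plan says.** Protocol 10.1 sorts nintedanib patients by their status when they join:

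- Group A started after 23 January 2017 and "have permanently discontinued the drug (as decided by the investigator) at the time of participation in the active surveillance". For this group, "Data for these patients will be collected in anonymized manner after getting approval from the Ethics Committees for data collection and sharing".
- Group B started after the same date and "are continuing the drug at the time of participation in the active surveillance".
- Group C is "Patients who have been newly prescribed nintedanib at the time of participation in the active surveillance".

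Protocol 10.2.2.1 applies the consent criterion to Groups B and C only. For the record-based groups it asks for "Patients in whom data collection is possible from the medical records (applicable for Group A and B patients"). No exclusion criterion concerns death. Protocol 10.9 states the intent: "The possible selection bias will be minimised by enrolling all patients who have initiated or will initiate nintedanib (Group A, B and C").

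Death is an SAE under Protocol 12.1, and SAE incidence is one of the two primary outcomes (Protocol 10.3.2, SAP 5.1).

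The SAP is narrower. Section 6.1 defines Groups B and C, not A, and has records screened for Group B only. In 6.3 the Screened Set consists of patients with a signed consent form. The Entered Set is drawn from it, and the Treated Set, which carries the primary analysis, from the Entered Set. Violation A1.2 in 6.2 removes patients whose form is absent, late or undated from all sets. Section 7.4 runs time at risk from the treatment start date. Section 4 declares no change from the protocol's planned analysis.

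**The concern.** A patient who started nintedanib after launch and died on it before the site enrolled anyone is neither continuing nor newly prescribed. Only Group A is left, and its definition does not mention death. Sites could classify the same history differently. Under the SAP, even a site that entered the death under Group A would see it dropped from the analysis.

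Retrospective enrolment is then conditional on survival, but the denominator is not. A Group B patient enrolled six months after starting brings six months of person-time that carried no possibility of an observed death. This is immortal time. It bears on the most serious SAE, in a disease that Protocol 8 describes in these words: "it is a rare and fatal disease with a median survival time of 2 to 3 years following diagnosis". According to Protocol 8, the surveillance exists because the regulator waived a local trial and only 20 Indian patients had received the drug in the two phase III trials. An understated fatal rate would defeat much of its purpose.

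**Working it through.** **Can the death enter the cohort?**

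| Step | Text | Patient who died on drug before enrolment |
|---|---|---|
| Group B | Protocol 10.1 | Cannot qualify: not continuing |
| Group C | Protocol 10.1 | Cannot qualify: not newly prescribed |
| Group A | Protocol 10.1 | Unclear: death is neither named nor excluded |
| Consent criterion | Protocol 10.2.2.1 | Does not apply to Group A |
| Groups analysed | SAP 6.1 | Group A absent |
| Screened, Entered, Treated Sets | SAP 6.3 | No signed form, so in none of them |
| Violation A1.2 | SAP 6.2 | Absent or late form: out of all sets |

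The absence of Group A is not one broken table. SAP 6.1, 6.7, 7.8.1 and violation A1.3 all treat Group B as the only record-based group. A legally authorised representative may sign the form, but nothing extends this to a patient already dead.

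No other procedure recovers the event. The vital-status call in Protocol 10.1 follows loss to follow-up, the rule on SAEs the investigator becomes aware of covers enrolled patients, and the site log in 10.2.3 covers included patients.

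**How long can the lag be?** From 23 January 2017 to the third amendment (13 June 2018), which opened retrospective enrolment, is 506 days. To version 5.0 (1 August 2018) is 555 days, or 18.2 months. SAP 3 says that six subjects entered under version 2.0 and the rest under 5.0. A Group B patient who started before August 2017 and joined under 5.0 had therefore already survived the whole 52-week window: a full year of denominator with no possible death. These are longest lags, not typical ones.

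**Illustration of the rate.** The documents give no figure for this bias, so there is none to reproduce. Assumptions:

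- the 2 to 3 year median, stated from diagnosis, applies from treatment start;
- the hazard is constant;
- every death is on drug;
- deaths before enrolment are not captured;
- 52 weeks is taken as 1 year.

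Formulas, with lag L in years from treatment start to enrolment:

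- λ = ln 2 / median, which gives 34.7 (2 y) or 23.1 (3 y) deaths per 100 patient-years
- dead before enrolment = 1 − exp(−λL)
- observed deaths per enrolled survivor, d = 1 − exp(−λ(1 − L))
- person-years under the SAP rule = L + d/λ
- observed fatal rate = 100 × d / (L + d/λ)

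For L = 0.5 and a 2-year median, d = 0.159 and person-years = 0.5 + 0.159/0.347 = 0.959. The rate is 16.6, and 16.6/34.7 = 48%.

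| L (years) | Dead before enrolment (2 y / 3 y) | Observed fatal rate (2 y / 3 y) | Share of true rate |
|---|---|---|---|
| 0.25 | 8.3% / 5.6% | 25.1 / 17.0 | 73% |
| 0.50 | 15.9% / 10.9% | 16.6 / 11.2 | 48–49% |
| 0.75 | 22.9% / 15.9% | 8.4 / 5.7 | 24% |
| 1.00 | 29.3% / 20.6% | 0 / 0 | 0% |

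The last column hardly depends on the assumed survival; it is close to 1 − L.

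For 200 patients with L = 0.5 and an assumed retrospective share (without the gap: 58.6 or 41.3 expected deaths, rates 34.7 or 23.1):

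| Retrospective share | Expected deaths (2 y / 3 y) | Fatal rate (2 y / 3 y) |
|---|---|---|
| 25% | 51.9 / 36.4 | 29.7 / 19.9 |
| 50% | 45.2 / 31.5 | 25.1 / 16.9 |
| 75% | 38.5 / 26.7 | 20.7 / 14.0 |

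**The case against.** The best defence is that the protocol already lets these patients in. The bracket in Group A can mean that the investigator judges whether stopping was permanent, not that the investigator ordered it. Protocol 10.1 leaves treatment duration to the treating physician, and nothing suggests that patients who stopped on their own are shut out. Death ends treatment for good. Group A needs no consent, its data come from anonymised records, and 10.9 intends all initiators to be enrolled.

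This stands as far as it goes. A reader might infer that the protocol excludes these patients from all three groups, and the documents do not support that: Group A is ambiguous, not closed. But the stated intent does not tell a site how to classify a death, and the SAP blocks the wider reading whichever way the site decides.

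A second defence is that Protocol 10.9 already admits a limitation: "For retrospective data, there may be a possibility of missed information on adverse events". That concerns event information missing for enrolled patients, not patients missing from the cohort.

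A third is that the mortality percentages do not measure the bias. That is correct. They count deaths from any cause, use survival from diagnosis, and treat every death as on drug. A patient who stopped nintedanib and later died fits Group A in Protocol 10.1 on any reading.

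**Conclusion.** The concern holds, and the firm part of it lies in the SAP. Protocol 10.1 leaves death on nintedanib before enrolment unclassified. The SAP, followed as written, keeps such deaths out of the primary SAE incidence while keeping retrospectively enrolled survivors' person-time from treatment start. Both effects push the fatal and total SAE rates down.

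The size cannot be fixed from the documents, which give neither the retrospective share nor the distribution of lags. Under a constant hazard and a 52-week cap, a six-month lag roughly halves the observed fatal rate among retrospectively enrolled patients. The effect on the whole cohort shrinks with their share. Total SAE incidence would fall by less in relative terms, because survivors' earlier non-fatal SAEs can still be found in the records; that fall is not quantified here. It would be tempting to read 11–16% by six months, or 21–29% by one year, as the proportion of fatal SAEs lost. Those figures only illustrate mortality.

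The point should be settled before analysis, since the SAP would otherwise carry it into a primary outcome.

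**What to change.** 1. In Protocol 10.1, state that Group A covers permanent discontinuation for any reason, including death before participation, with the death recorded as an SAE.
2. In the SAP, restore Group A in 6.1 and in the sections that describe record review. Exempt it from the consent-form requirement in 6.3 and from violation A1.2, so that these patients reach the Treated Set. Rewording the protocol alone would put no death into the primary analysis.
3. Have sites count, and the report show, how many screened initiators died before enrolment.
4. Add a sensitivity analysis with time at risk and events counted from enrolment (delayed entry), or restricted to Group C. Under delayed entry, Group A contributes nothing and Group B contributes only its time after joining.

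A parallel change to Group I would not help SAE incidence, because pirfenidone patients are not followed.

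The cost is a clarifying phrase in the protocol, a small SAP revision covering the groups and sets, and some extra record abstraction. The abstraction falls within the anonymised collection, subject to Ethics Committee approval, that is already planned for Group A.

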12. MANAGEMENT AND REPORTING OF ADVERSE EVENTS/ADVERSE REACTIONS

12.1 DEFINITIONS OF ADVERSE EVENTS

Adverse event

An adverse event (AE) is defined as any untoward medical occurrence in a patient or clinical investigation subject administered a medicinal product and which does not necessarily have a causal relationship with this treatment. An adverse event can therefore be any unfavourable and unintended sign (e.g. an abnormal laboratory finding), symptom, or disease temporally associated with the use of a medicinal product, whether or not considered related to the medicinal product.

Adverse reaction

An adverse reaction is defined as a response to a medicinal product which is noxious and unintended. Response in this context means that a causal relationship between a medicinal product and an adverse event is at least a reasonable possibility. Adverse reactions may arise from use of the product within or outside the terms of the marketing authorisation or from occupational exposure. Conditions of use outside the marketing authorization include off-label use, overdose, misuse, abuse and medication errors.

Serious adverse event

A serious adverse event is defined as any AE which

- results in death,
- is life-threatening,
- requires in-patient hospitalization, or
- prolongation of existing hospitalisation,
- results in persistent or significant disability or incapacity, or
- is a congenital anomaly/birth defect

Life-threatening in this context refers to an event in which the patient was at risk of death at the time of the event; it does not refer to an event that hypothetically might have caused death if more severe.

Medical and scientific judgement should be exercised in deciding whether other situations should be considered serious adverse events, such as important medical events that might not be immediately life threatening or result in death or hospitalisation but might jeopardise the patient or might require intervention to prevent one of the other outcomes listed above. Examples of such events are intensive treatment in an emergency room or at home for allergic bronchospasm, blood dyscrasias or convulsions that do not result in hospitalisation or development of dependency or abuse.

No adverse events of special interest (AESI) have been defined for this active surveillance.

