12.2 ADVERSE EVENT AND SERIOUS ADVERSE EVENT COLLECTION AND REPORTING

The investigator shall maintain and keep detailed records of all AEs in their patient files.

Collection and Reporting of AEs

The design of this active surveillance is of non-interventional nature and will be conducted within the conditions of the approved marketing authorisation. Sufficient data from controlled interventional trials are available to support the evidence on the safety and efficacy of the studied BI drug. For this reason the following AE collection and reporting requirements have been defined.

The following information must be collected for Group A,B and C patients from the date of initiation of nintedanib until individual patient's end of study:

- All ADRs associated with nintedanib
- All SAEs in patients exposed to nintedanib

All ADRs and SAEs including those persisting after study completion must be followed up until they are resolved, have been sufficiently characterized, or no further information can be obtained.

The investigator carefully assesses whether an AE constitutes an ADR using the information below.

Causal relationship of adverse event:

The definition of an adverse reaction implies at least a reasonable possibility of a causal relationship between a suspected medicinal product and an adverse event. An adverse reaction, in contrast to an adverse event, is characterised by the fact that a causal relationship between a medicinal product and an occurrence is suspected.

Medical judgment should be used to determine the relationship, considering all relevant factors, including pattern of reaction, temporal relationship, de-challenge or re-challenge, confounding factors such as concomitant medication, concomitant diseases and relevant history.

Arguments that may suggest **a reasonable causal relationship** could be:

- The event is **consistent with the known pharmacology** of the drug
- The event is known to be caused by or **attributed to the drug class**.
- A **plausible time to onset of the event** relative to the time of drug exposure.
- Evidence that the **event is reproducible** when the drug is re-introduced
- **No medically sound alternative etiologies** that could explain the event (e.g. pre-existing or concomitant diseases, or co-medications).
- The event is typically **drug-related and infrequent in the general population** not exposed to drugs (e.g. Stevens-Johnson syndrome).

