## **6.7 BASELINE, TIME WINDOWS AND CALCULATED VISITS**

Values observed at visit 1 will be considered as baseline assessment.

The medical records of patients belonging to Group B will be evaluated in the nintedanib treated arm till the date of start of their participation in this active surveillance program. Group B and Group C patients will be followed up according to clinical practice for at least 52 weeks or up to the discontinuation (whichever is earlier) from the start of the treatment at regular intervals (i.e. approximately every 4 weeks for the first 3 visits and approximately every 12 weeks thereafter till week 52).

There may be unscheduled visit(s) between the scheduled visits. In case the patient is lost to follow up (patient not contactable for further visits), the site should attempt to contact the patient telephonically to gather the information on the vital status and record it in the eCRF. Patients who are prescribed pirfenidone will not be followed.

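### The telephone call to patients lost to follow-up asks only for vital status, so non-fatal SAEs, ADRs and nintedanib stopping after the last visit are not actively sought

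*Protocol*

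**What the plan says.** **The call.** For a patient who can no longer be contacted for visits, Protocol 10.1 tells the site to try to reach the patient or a relative by telephone "to gather the information on the vital status and record it in the eCRF". SAP 6.7 says "the site should attempt to contact the patient telephonically to gather the information on the vital status and record it in the eCRF" and does not mention a relative. Neither names any other purpose.

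**Reporting duties around it.** The next paragraph of Protocol 10.1 makes an event reportable under 12.2 "whenever the investigator becomes aware of SAEs and/or ADRs occurring in an enrolled patient before individual patient's end of study". Protocol 12.2 sets the collection period for ADRs and SAEs as running "from the date of initiation of nintedanib until individual patient's end of study". Protocol 12.1 counts an event as serious if it "results in death", so the vital-status question does pick up fatal SAEs.

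**The outcomes.** Protocol 10.3.2 and SAP 5.1 make the incidence of ADRs and of SAEs primary. The secondary outcome is the share of patients whose nintedanib was reduced, interrupted or stopped because of an adverse event.

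**The analysis.** SAP 6.3 analyses all outcomes in the Treated Set (eligible patients with at least one dose). SAP 6.6 imputes nothing except adverse event onset dates. SAP 7.4 reports both percentages and rates per 100 patient-years. For patients without the event, time at risk runs to an end date that the SAP does not define.

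**Acknowledged limitation.** For prospective follow-up, Protocol 10.9 says that "lost to follow up, loss of information and recall bias could impose limitations". It gives no expected rate, direction or size.

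**The concern.** At scheduled and unscheduled visits the protocol expressly calls for ADRs and SAEs to be collected. The call to a lost patient is the one contact whose stated purpose is narrower. A duty to report what one becomes aware of does not make anyone ask. A non-fatal hospital admission elsewhere, a reaction managed by another doctor, or nintedanib stopped because of an adverse event can stay unknown even when someone answers the telephone.

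The analysis then treats silence as absence. A lost patient stays in the denominator and counts as event-free after the last visit. This study exists to estimate how often ADRs and SAEs occur, so the error goes directly into its main results. It concerns the prospective follow-up of Groups B and C.

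**Working it through.** **Textual check.** No section of the current protocol or SAP text tells the caller to ask about non-fatal SAEs, ADRs, or the date or reason of stopping. Protocol 10.3.1 and SAP 7.7 let exposure end at final contact when no stop date is known. That closes the exposure record but supplies neither the true stop date nor the reason.

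**Size.** The plan states no loss rate or event rate, so there is no figure to reproduce. From the documents: *N* = 200 (Protocol 10.5) and a 52-week horizon. Everything else is assumed:

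- exponential time to first event, 52-week risk *p* = 30% in retained patients;
- a share *L* lost, all at mid-year (0.5 year), and still on nintedanib to week 52, so that later events would count;
- hazard after loss *k* = 1, 2 or 3 times that of retained patients;
- events before loss recorded, none after loss captured.

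Hazard: *h* = −ln(1 − 0.30) = 0.357 per year. Risk in the first half-year: 1 − exp(−0.5*h*) = 0.163.

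Observed = (1 − *L*)·*p* + *L*·(1 − exp(−0.5*h*))

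True = (1 − *L*)·*p* + *L*·(1 − exp(−0.5*h* − 0.5*kh*))

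For *L* = 0.10: observed = 0.90 × 0.30 + 0.10 × 0.163 = 28.6%. With *k* = 3, true = 0.90 × 0.30 + 0.10 × 0.510 = 32.1%.

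| Lost | *k* | True % | Observed % | Gap (points) | Patients of 200 with first event missed |
|---|---|---|---|---|---|
| 5% | 1 | 30.0 | 29.3 | 0.7 | 1.4 |
| 10% | 1 | 30.0 | 28.6 | 1.4 | 2.7 |
| 10% | 2 | 31.1 | 28.6 | 2.5 | 5.0 |
| 10% | 3 | 32.1 | 28.6 | 3.5 | 6.9 |
| 20% | 1 | 30.0 | 27.3 | 2.7 | 5.5 |
| 20% | 3 | 34.2 | 27.3 | 6.9 | 13.9 |

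At 60% risk, the range from 5% lost at equal hazard to 20% lost at triple hazard is 2.3 to 18.9 patients missed.

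**Rate per 100 patient-years**, under the same assumptions with 10% lost. Person-years per patient if time stops at the last visit: 0.90 × 0.30/0.357 + 0.10 × 0.163/0.357 = 0.803. Rate = 100 × 0.286/0.803 = 35.7.

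If instead time runs on to a call at week 52 with no events sought, add 0.10 × 0.837 × 0.5 = 0.042 person-years. Rate = 100 × 0.286/0.845 = 33.9.

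| *k* | True rate | Censored at last visit | Time run on to the call |
|---|---|---|---|
| 1 | 35.7 | 35.7 | 33.9 |
| 2 | 37.2 | 35.7 | 33.9 |
| 3 | 38.4 | 35.7 | 33.9 |

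The percentage is therefore low in every row. The rate is correct when loss is non-informative and time stops at the last visit, and low otherwise. Which column applies cannot be read from the SAP.

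**The case against.** The strongest defence is that nothing is barred. Deaths are captured, an event mentioned in the call must be reported, and Protocol 12.2 says ADRs and SAEs must be collected to the patient's end of study. This stands: the gap is a missing prompt, not a prohibition.

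A reader might infer that the lost patients are those most likely to have had an event. That is plausible, but no section gives reasons for loss or event risk after it. The shortfall in the percentage does not need this assumption; the shortfall in the rate does, unless time at risk runs on to the call.

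A reader might also take every event in lost patients as missing. With triple the 30% risk that gives 0.10 × 0.90 = 9 points at 10% lost and 0.20 × 0.90 = 18 points at 20%. The documents do not support this, because events recorded before loss count and the call finds deaths.

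Three practical objections stand in part:

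- The call is only an attempt, to people already hard to reach, and a relative may not know onset dates, drug attribution or why treatment stopped. This limits the yield but is no reason not to ask.
- SAP 7.8.1 ends the treatment-emergent window at 52 weeks, discontinuation or final contact at the last regular observation. An event learned by telephone might fall outside it, so extra questions alone are not enough.
- The flow chart and eCRF are not in the public text, so a prompt there cannot be ruled out. Nothing is inferred from their absence.

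Finally, Protocol 10.9 discloses loss to follow-up. Disclosure is proper for a descriptive study, but it does not replace a question that could be asked in a contact already planned.

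**Conclusion.** The point holds as a gap in active enquiry. After the last visit, non-fatal SAEs, ADRs and the date and reason of stopping nintedanib are not sought from lost patients, although they are primary and secondary outcome data. The percentages are low even when loss is unrelated to events. The patient-year rate is low only if loss is informative or if time at risk runs on to the call.

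At 30% risk with mid-year loss, the percentage is about 1.4 to 3.5 points low with 10% lost, and up to about 7 points low with 20% lost at triple hazard. All loss rates, risks and hazard multiples are assumptions. The figures also take nothing after loss as captured, so they somewhat overstate the gap where the call finds deaths.

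Protocol section 6 records that the first amendment introduced telephone collection of safety information. That is superseded text and is not counted as a contradiction.

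**What to change.** 1. **Protocol 10.1 and SAP 6.7.** Have the same call attempt ask the patient or relative for vital status and, in addition, hospitalisation or any other SAE, suspected reactions, and the date and reason of nintedanib discontinuation, with onset dates where known. Name the relative in the SAP as the protocol does.
2. **SAP 7.4 and 7.8.1.** Define the end of time at risk for lost patients. If the call succeeds, count call-reported events and person-time together, up to 52 weeks or discontinuation, whichever is earlier. If it fails, censor at last contact. Align the treatment-emergent window with this. Under SAP 6.6 a wholly unknown onset date is imputed no later than the last visit, so state how such call-reported events are handled.
3. **Reporting.** Give the number lost, and show percentages and rates with and without call-reported events.

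The cost is a few questions in a contact already planned, one set of eCRF fields and a short SAP definition, with no extra visit or call. The drawback is that telephone and relative reports are less well documented; showing results both ways lets the reader judge their influence.
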